Several studies have shown a reduction of the sympathetic activity measured by microneurography (MSNA) after an exercise training program in heart failure [19, 20]. This is also found on other ANS parameters such as the Heart Rate Variability that is improving [6, 9]. Catecholamines also tends to decrease with aerobic activity [21]. This improvement in vegetative balance is associated with an improvement in the different vegetative reflexes involved in the regulation of cardiovascular ANS. Thus, the abnormalities noted on the baroreflex, the chemoreflex, the ergoreflex and the central control are all potentially improved by repeated aerobic exercise [22, 23]. Thus the sympathetic stimulation induced during the exercise is followed by a period of increase in vagal tone, explaining the benefit on the rhythmic profil . To our knowledge there is no study comparing the effects on the ANS of MICE training versus HIIT training in CHF.

Hypothesis

Our team recently used an intermittent exercise protocol that has been optimized in CHF patients [24] in order to induce a strong cardiovascular and muscular stimulus while ensuring safety and comfort of the patient (30 seconds at 100% of peak power alternate with 30 sec of passive recovery). In 18 CHF patients, we showed that a single intermittent exercise session increases parasympathetic tone (high frequency index in normalized units HFnu%) and significantly decreases premature ventricular contraction within the 24h of the exercise, compared to a single session of MICE [16]. These results appear promising and suggest that stimuli associated with intense intermittent exercise and passive recovery, as opposed to continuous-type exercise of moderate intensity, would be more effective to increase sympatho-vagal balance and arrhythmias. Nevertheless, the effects of a several weeks of an HIIT program on explanatory parameters of sudden death (SNA activity, arrhythmias, cardiac function) have never been studied in CHF patients. We therefore hypothesize that HIIT is superior to MICE for 1/ increasing parasympathetic activity measured by HRV, 2 / the cardiorespiratory fitness. In addition, we also hypothesize that there is a link between improved physical capacity and vagal tone and decreased arrhythmias.

Objectives

Main objective:

To compare, in patients with chronic heart failure, the efficacy of 4-weeks exercise training programs (MICE vs HIIT) on the evolution of the spectral high frequency (HF) component of HRV.

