The rehabilitation program focus on controlling cardiovascular risk factors, diet monitoring, therapeutic education sessions and psychological support when needed. In our clinical center, the RP last 3 hours per day, 5 days per week during 3.5 weeks. The daily activity training include a cycling endurance training (HIIT or MICT), a 30-min of gymnastics or muscle strengthening (3 series of 15 repetitions at 50% of 1-repetition maximum test in chest press, leg press, pull over, low row, leg extension) and 45-min outside walking sessions. Each session will be monitored by a physiotherapist and was supervised by a cardiologist.

The HIIT consist of two sets of 8-min intervals at 100% of peak power output (PPO) [24, 26]. Each interval set is composed of repeated bouts of 30 s at 100% of PPO interspersed by 30 s of passive recovery in the seated position. Four minutes of passive recovery are allowed between the two sets. The MICT training consist of cycling 30 minutes at 60% of peak power output. Each mode of training start with 5 minutes of warm up and finish with 5 minutes of cool down at 30% of PPO.

Primary and secondary endpoints

Primary endpoint

Evolution between day 0 (D0) and Week 4 (W4), of the High Frequency component of HRV measured during the night time period and expressed in normalized units (%): HF nu%.

Secondary Endpoint

The analysis will also focus on the evolution of the following variables:

Variables extracted from the analysis of the HRV (Holter-ECG 24h)

Heart Rate rest (beats per minute - bpm)

LF, HF (milliseconds², standard units)

VLF (milliseconds²)

Total Spectral Power (milliseconds²)

SDNN (milliseconds)

rMSSD (milliseconds)

LF / HF ratio

Number and nature of arrhythmias

Variables of echocardiography

Size of the cardiac cavities (diameter (mm), surface (cm²), volume (ml.m²))

LV systolic function (Ejection fraction (%), parietal thickness (mm))

Filling LV (E / A, E / e', Ap-Am (ms), E / Vp)

Systolic function of RV (shortening fraction (%), S'wave (cm.s), systolic excursion of tricuspid ring (mm))

Variables of the cardiopulmonary exercise test

Maximum oxygen consumption (VO₂pic (ml.min))

Maximum heart rate (bpm)

Heart rate after 1 minute, 2 minutes and 3 minutes of passive recovery

Oxygen pulse (ml.min.batt)

Slope VE / VCO₂

Maximum aerobic power (watts)

Variables of endothelial function

Reactive Hyperemia Index (RHI)

Variables of the blood test

Blood glucose (mmol.L); HbA1c (%)

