If HIIT is more interesting to improve ANS activity, arrhythmias, cardiac function and cardiorespiratory fitness (all are parameters of sudden cardiac death), then the optimization and the prescription of this type of exercise training would be important. That would demonstrate the great interest and the feasibility of an intense exercise training program specific to chronic heart failure patients. This prescription could later be transposable at home for a long term period of practice. Thus this study will open the field to other research perspectives in particular in terms of longer-term impact on the mortality that remains to be evaluated.

Statistics

Sample Size

The primary outcome measure is the change of High Frequency power in normalized units (HFnu) measure at night as a surrogate of cardiac parasympathetic modulation. Based on our first study [16], we hypothesise that HIIT mode will induce a ~11% change in HFnu compare to MICT training mode. With a mean value of the main criteria (HFnu %) of 31.5%, a standard deviation of 3%, a statistical power (1- β) to 90% and a α risk set to 0.05 in bilateral hypothesis, 16 patient per group must be recruited.

Statistical analyses

Data will be summarized by mean \pm standard deviation (SD) for continuous variables; percentages and frequencies for categorical ones. Shapiro-Wilk and Bartlett tests will be used to assess normality and equality of variance among variables analysed, respectively. Baseline inclusion characteristics will be compared between groups using one-way ANOVA or Mann-Whitney non-parametric test for quantitative variables. Changes within groups (difference between post and pre training values) will be analysed using a paired t-test for normally distributed data or paired Wilcoxon signed-rank test for non-normally distributed data. To analyse the differences between HIIT and MICT groups, repeated ANOVA analysis will be carried out estimating time effect (post vs pre), group effect (HIIT vs MICT) and the interaction time x group. P value <0.05 will be considered as significant. Correlation between parameters will be analyzed using the Pearson Correlation Test or Spearman's Rank Correlation Test, depending on the nature of the conditional distribution and the shape of the relation.

Research Calendar

Provisional schedule

Beginning of inclusions: June 2015

Duration of the inclusion period: 1 year

Duration of participation of each patient: 7 months (4 weeks in rehabilitation centre)

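### The 16 per group is computed correctly, but the primary between-group test is a change-score test; adjusting Week 4 HFnu for D0 HFnu would be more precise at almost no cost

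*Combined protocol and SAP*

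**What the plan says.** The Primary endpoint section defines a change: "Evolution between day 0 (D0) and Week 4 (W4), of the High Frequency component of HRV", measured at night in normalized units. The Sample Size section agrees: "The primary outcome measure is the change of High Frequency power in normalized units (HFnu) measure at night".

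That section takes its effect from an earlier study by the same team: "Based on our first study [16], we hypothesise that HIIT mode will induce a ~11% change in HFnu", relative to moderate continuous training. It then gives "With a mean value of the main criteria (HFnu %) of 31.5%, a standard deviation of 3" percent, 90% power and a two-sided alpha of 0.05, and concludes "16 patient per group must be recruited". It does not say whether the SD is that of HFnu at one visit or of the change. No correlation between D0 and Week 4 values is given anywhere.

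Under Statistical analyses, the arms are compared by repeated ANOVA with a time effect, "group effect (HIIT vs MICT) and the interaction time x group". The decision rule is "P value <0.05 will be considered as significant". No baseline-adjusted model and no confidence interval are named. The Holter recording is scheduled at both D0 and Week 4 in the follow-up table. The final stop rules say that patients who stop permanently are not replaced and that their data are left out of the analysis.

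**The concern.** With one measurement before training and one after, the time x group interaction tests exactly what a two-sample t-test on the individual changes tests. Subtracting the D0 value in full removes stable differences between patients, but it also brings in all the noise of the D0 measurement. When D0 and Week 4 are only moderately correlated, that is a poor exchange. Regressing Week 4 on D0 lets the data decide how much of the baseline to subtract.

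At stake is the precision of the primary comparison in a trial of 32 patients. The plan already collects the baseline value needed to improve it but does not use it in the most efficient way. There is also a link to the stated power. The change test depends on the SD of the change, whereas the SD in the Sample Size section stands beside a mean of 31.5, which is an HFnu level. A reader cannot tell whether the 90% belongs to the test that will be run.

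**Working it through.** **Inputs from the Sample Size section:** mean 31.5, difference 11%, SD 3, two-sided alpha 0.05, power 90%, 16 per group. **Assumed, because the documents do not give it:** rho, the correlation between D0 and Week 4 HFnu, with equal SDs at the two visits.

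**Step 1. Reproduce the plan's figure.**
- Difference = 0.11 × 31.5 = 3.465 points.
- n per group = 2 × (1.960 + 1.2816)² × (3 / 3.465)² = 15.75, rounded up to 16.
- Power at 16: 90.4% by the normal approximation, 88.5% by the t-test (17 per group would give 90.4% by t).
- Read as 11 absolute points, the same formula gives 1.6 per group. Only the relative reading leads to 16.

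**Step 2. Variance under the two analyses.** Let S be the SD at one visit.
- Change: SD = S × √(2(1 − rho)).
- Week 4 adjusted for D0: residual SD = S × √(1 − rho²).
- Ratio of variances, adjusted to change: (1 − rho²) / (2(1 − rho)) = (1 + rho) / 2, that is 0.65 at rho 0.3, 0.75 at 0.5 and 0.85 at 0.7. It never exceeds 1.

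**Step 3. Power at 16 per group if 3 is the SD at one visit.** The change test uses the t-test. ANCOVA power comes from simulation with the covariate slope estimated, so it includes the lost degree of freedom and chance baseline imbalance.

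| rho | SD of change | Planned test | Residual SD | ANCOVA |
|---|---|---|---|---|
| 0 | 4.24 | 61% | 3.00 | 87% |
| 0.3 | 3.55 | 76% | 2.86 | 90% |
| 0.5 | 3.00 | 88.5% | 2.60 | 95% |
| 0.7 | 2.32 | 98% | 2.14 | 99% |

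**Step 4. Power at 16 per group if 3 is the SD of the change.** The planned test has 88.5% whatever rho is. The residual SD for ANCOVA is 3 × √((1 + rho)/2).

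| rho | Residual SD | ANCOVA |
|---|---|---|
| 0.5 | 2.60 | 95% |
| 0.7 | 2.77 | 92% |
| 0.8 | 2.85 | 90% |
| 0.95 | 2.96 | 88% |

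**Step 5. The cost.** ANCOVA has 29 rather than 30 degrees of freedom at 16 per group, and estimating the slope inflates the variance by about 1/28 (3.6%). If 3 is the SD of the change and rho is near 1, nothing is gained in exchange: power goes from 88.5% to 87.3% at 16 per group, about 1 point. At 12 per group it goes from 77.2% to 75.0%, about 2 points.

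**Step 6. Number analysed.** Sixteen is both the number required and the number recruited. If 3 is the SD of the change, t-test power for the planned analysis is 86.3% with 15 analysed per group and 83.7% with 14. If 3 is a single-visit SD and rho is 0.6, 14 analysed per group still give about 91%. Whether losses erode the 90% therefore depends on what SD 3 describes.

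**The case against.** The strongest reply is that nothing here is wrong. The arithmetic reproduces, the trial is randomised, and the interaction is a valid test of the endpoint as defined. If 3 is the SD of the change, the planned test has essentially the stated power. If 3 is a single-visit SD, a material shortfall needs rho clearly below 0.5, and the documents give no sign that it is. The gain from adjustment is also small where rho is high: 98% to 99% at rho 0.7 on the single-visit reading, and nothing or a slight loss near rho 0.95 on the change reading.

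All of that stands, and it limits the point to efficiency. What it does not answer is that the large gains occur where the planned test is weakest, while the worst loss is about 1 point at the planned size. Since rho is unknown at the design stage, that balance favours adjustment.

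A reader might go further and infer that the trial is underpowered. The documents do not support this: the true power may lie above or below 90%. A reader might also infer that the SD is a short-term quantity, because the Hypothesis section describes the team's earlier work so: "In 18 CHF patients, we showed that a single intermittent exercise session increases parasympathetic tone". But the Sample Size section ties that study to the 11% effect and does not say where the SD comes from, so no power figure can be built on that inference.

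**Conclusion.** The point holds as an efficiency improvement to the primary analysis, not as an arithmetic error. The 16 per group is correct for the stated inputs, and the planned test is valid. Adjusting Week 4 HFnu for D0 has (1 + rho)/2 times the variance of the change. Under both readings of SD 3, power at 16 analysed per group is then at least about 87%, whereas the planned test can be as low as 61% if 3 is a single-visit SD and rho is 0. This rests on the 3.465-point difference, on equal SDs at the two visits, on rho between 0 and 1, and on 3 being either the single-visit SD or the SD of the 4-week change. The floor does not guarantee 90% and does not apply if 3 is some other quantity.

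The 90% in the plan is unconfirmed for the change test. Nor does the missing confidence interval make a null result unreadable: an interval could be derived from the means and SDs of the changes. It should simply be planned. Nothing here shows that more than 16 per group are needed.

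**What to change.** 1. Amend Statistical analyses so that the primary between-group test compares night-time HFnu at Week 4 adjusted for HFnu at D0 (ANCOVA), in place of the repeated ANOVA interaction, and report the adjusted difference with its 95% confidence interval. The cost is a protocol/SAP amendment and one degree of freedom. The Holter recordings are already scheduled, so no visit or measurement is added.

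2. When revising Sample Size for this model, say that 11% is relative (3.465 points), say what SD 3% describes (with the D0 to Week 4 correlation if it is a single-visit SD), and restate the power for the number expected to be analysed, since permanent stoppers are neither replaced nor analysed. This is wording and a recalculation; the result may be above or below 90%. Whether to recruit beyond 16 per group should be decided only once that figure is known.

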Total duration of the research: 3 years

Summary table of patient follow-up

	Pre-inclusion D- 1 à D- 2	Inclusion D 0 +/- 2 days	Week 4 +/- 3 days
eligibility criteria	✓		
Patient information of the research	✓		
Collection of sign informed consent		✓	
Randomization		✓	
Clinical Exam ¹ (Nurse)		✓	✓
Holter ECG-24h (nurse)		✓	✓
Endothelial function (nurse)		✓	✓
Biological assessment 2 (nurse)		✓	✓
Echocardiography (cardiologist)		✓	✓
Cardiopulmonary exercise test (cardiologist)		✓	✓

¹Clinical examination: measurement of: height, weight, analysis of body composition by impedance, measurement of waist circumference and resting blood pressure.

²Biological assessment: lipid balance, glycemic, adrenaline, norepinephrine, NT-pro-BNP, beta hCG for women(D0).

Specific terms of monitoring

In addition to the usual medical care of the patient, a Supervisory Committee will ensure the proper conduct of research, the safety of proposed programs. , Any adverse effects caused by physical exercise training (muscle pain cramp, fatigue of the patient), change of drug treatment, compliance with the protocol will be noted in the medical file. In case of fatigue of a patient or for medical or paramedical reason, the exercise training intensity may be reduced or even removed. In this case, any changes to the exercise training program will be documented in the medical file.

Rules for stopping research

The rules for temporary cessation of the participation of a person in research or part or all of the research:

- 1) Anyone is free to temporarily stop participating in the research at any time.
- 2) Anyone can ask to temporarily interrupt their participation due to side effects of physical activity (pain, muscle fatigue ...).
- 3) Anyone may be temporarily unavailable for personal reasons.
- 4) A person who has not missed more than 3 consecutive sessions on the 4 weeks of the rehabilitation program can maintain their participation in the research if they wish.
- 5) The Supervisory Committee has the possibility to stop the search

The final stop rules:

- 1) Anyone is free to permanently stop his participation in research at any time without having to give reason.
- 2) Anyone with an incapacitating health problem that prohibits the practice of a physical activity will be excluded from research by decision of the investigator who will inform the coordinator, the rehabilitation team and the research manager.

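### The 90% power is attached to 16 patients per group recruited, but 16 is the number that must be analysed, and permanent stoppers are neither replaced nor analysed

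*Combined protocol and SAP*

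**What the plan says.** The primary endpoint is a change that needs a Week 4 value: "Evolution between day 0 (D0) and Week 4 (W4), of the High Frequency component of HRV", measured at night in normalised units. Statistics / Sample Size repeats this ("The primary outcome measure is the change of High Frequency power in normalized units (HFnu") and gives the effect: "we hypothesise that HIIT mode will induce a ~11% change in HFnu compare to MICT training mode". The other inputs are "With a mean value of the main criteria (HFnu %) of 31.5%, a standard deviation of 3" (per cent), 90% power and a two-sided 0.05 level. The result is "16 patient per group must be recruited". The section states no loss rate, no inflation and no separate number to be analysed. The section headed Expected fallout concerns anticipated benefits, not attrition.

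Statistics / Statistical analyses plans a repeated-measures ANOVA that estimates a time effect, a "group effect (HIIT vs MICT) and the interaction time x group".

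The final stop rules give two routes to a permanent stop. One is voluntary: "Anyone is free to permanently stop his participation in research at any time without having to give reason". The other is the investigator's decision: "Anyone with an incapacitating health problem that prohibits the practice of a physical activity will be excluded from research by decision of the investigator". The text that follows these rules says that people who stop permanently will not be replaced and that the data will be left out of the statistical analysis. In context, these are the data of the people who stopped.

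**The concern.** A power figure belongs to the number of patients in the test. The plan ties it to the number recruited, while its own rules make the analysed number smaller each time someone stops permanently, and nothing can make it larger. If 16 already included a margin, this would not matter, so the question is whether it does.

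At stake is how the primary result will be read. In a trial of 32 patients, a null result will be set against the stated 90%. If patients have been lost, that figure describes a fuller data set than the one analysed.

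**Working it through.** **Inputs** (Statistics / Sample Size unless noted)
- Effect: about 11%, read as relative to the mean of 31.5, so 0.11 x 31.5 = 3.465 HFnu points. An absolute difference of 11 points would need only 2 per group, so the relative reading is the one that fits.
- SD: 3, used directly as the SD of the tested change.
- Two-sided level 0.05 (z = 1.960); power 90% (z = 1.2816).
- Allocation 1:1 (Design of the study).
- Loss rate: not given. The loss counts below are illustrative.

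**Step 1. Reproduce the plan's figure.**
n per group = 2 x (1.960 + 1.2816)² x (3 / 3.465)² = 15.75, rounded up to 16. The plan's figure is reproduced as a complete-data number. The only slack is the rounding from 15.75 to 16.

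**Step 2. Power at smaller analysed numbers.**
The standard error of the difference is 3 x sqrt(1/n1 + 1/n2). Power by the normal approximation is Φ(3.465 / SE − 1.960). With two time points, the time x group test is equivalent to a two-sample t-test on the change, so its power comes from the noncentral t with n1 + n2 − 2 degrees of freedom.

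| Analysed | SE | 3.465 / SE | Normal approximation | Time x group test |
|---|---|---|---|---|
| 16 vs 16 | 1.061 | 3.267 | 90.4% | 88.5% |
| 16 vs 15 | 1.078 | 3.214 | 89.5% | 87.4% |
| 15 vs 15 | 1.095 | 3.163 | 88.6% | 86.3% |
| 14 vs 14 | 1.134 | 3.056 | 86.3% | 83.7% |

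One loss per group is 1/16 = 6.25% of those recruited; two per group is 12.5%. At exactly the stated inputs, one lost patient out of 32 takes power just below 90% by the method that gave 16.

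**Step 3. Sensitivity to the rounded inputs.**
- Effect of 11.5% (0.115 x 31.5 = 3.62 points), SD 3, 15 vs 15: 91.1% by the normal approximation, 89.1% by the time x group test. At 14 vs 14: 89.2% and 86.8%.
- Effect of 10.5% (3.31 points), SD 3, time x group test: 85.5% at 16 vs 16 and 83.0% at 15 vs 15.
- Effect of 3.465 points, time x group test: an SD of 2.8 gives 90.5% at 15 vs 15; an SD of 3.2 gives 84.2% at 16 vs 16 with no loss.

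**Step 4. Sensitivity to what the SD describes.**
If 3 is the SD of a single HFnu measurement, the SD of the change is 3 x sqrt(2(1 − ρ)), where ρ is the D0 to W4 correlation. The documents do not give ρ. At ρ = 0.5 the SD of the change is again 3. At 14 per group, the time x group test has 76.6% power at ρ = 0.4, 90.8% at 0.6 and 96.7% at 0.7. It reaches 90% at a ρ of about 0.53 with 16 per group and about 0.59 with 14.

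**The case against.** The strongest reply is that the gap lies within the precision of the inputs. The effect is given as approximately 11% and the SD to one digit. By the normal approximation, an effect of 11.5% still gives 91.1% with 15 per group. By the time x group test, an SD of 2.8 gives 90.5% with 15 per group. If 3 is a level SD, power may lie on either side of 90%. All of this stands. A reader might infer that a single loss per group must bring power below 90% whatever the rounding. The documents do not support that: it holds for effects that round to 11% only if the t-based calculation is used and the SD is fixed at exactly 3.

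A second reply is that losses may be few. The programme lasts 3.5 weeks, each session is monitored, the assessments belong to usual follow-up, and temporary interruption and reduced intensity are allowed. With no permanent stops, the recruited and analysed sets coincide. This also stands, and it is why no particular shortfall can be claimed.

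A third temptation is to say that 90% is wrong even with complete data, because the time x group test gives 88.5% at 16 per group. That gap lies within the rounding of the effect (85.5% to 91.1% over 10.5% to 11.5%) and reflects a choice of approximation. It is not an error in the plan.

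None of these replies touches the labelling. The calculation yields an analysed number, the plan calls it a recruited number, and the stopping rules keep the two equal only if nobody stops permanently.

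**Conclusion.** Wrong as written; minor. Sixteen is correct as the number analysed per group and has no allowance for loss. The 90% therefore holds only if there are no permanent stops, which the plan itself provides for.

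At the stated inputs, one loss per group costs about 2 percentage points of power (90.4% to 88.6% by the normal approximation, 88.5% to 86.3% by the time x group test). Two per group cost about 4 to 5 points (to 86.3% and 83.7%). These sizes assume a difference of 3.465 points, an SD of exactly 3 for the D0 to W4 change, and loss counts chosen for illustration. The labelling fault is certain, but the size of any shortfall is not. A reader might infer that the trial is materially underpowered or that 16 was miscalculated; the documents support neither.

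**What to change.** In Statistics / Sample Size:
- State that 90% power applies to 16 patients analysed per group, that 16 per group will be recruited, and that permanent stoppers are not replaced.
- Give the power at the expected number analysed, or as a range if no loss rate can be justified, and name the method. By the method that gave 16, this is about 89% at 15 per group and 86% at 14. By the planned time x group test it is about 86% and 84%.
- Say whether 3 is the SD of the D0 to W4 change. If it is the SD of the HFnu level, state the assumed D0 to W4 correlation and give the matching power.

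The 90% may remain for the case of no loss, with its method named.

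The cost is a few sentences and a slightly less favourable stated power. No extra patients are needed and the stopping and exclusion rules are unchanged. The change makes the statement accurate; it does not restore any power lost through permanent stops.
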